ordering cognitive function and chronic pain after injury. The presumed link includes engagement of descending noradrenergic pathways. We will propose parallel clinical trials to examine the role of psychosocial factors on resolution of pain after surgery.

Context of this IRB application

As noted above, chronic pain after surgery is a major health problem and we have minimal understanding of whether cognitive and provocative pain testing factors associated with increased risk of this problem are mere associations or causations. We propose to test, within the context of a multi-investigator NIH application, whether chronic pain after surgery is caused by an inadequate response from descending inhibition and whether cognitive and psychosocial factors determine whether pain after surgery resolves or becomes chronic by controlling descending inhibitory tone.

We will submit a Program Project Grant application for the October, 2011 deadline and the purpose of this IRB application is to acquire preliminary data to demonstrate feasibility and allow an accurate power analysis for the size of the proposed study within that grant application.

Objectives

The objectives of this pilot effort are:

- 1) To demonstrate the feasibility of conducting this protocol in this clinical population. The execution of this study will allow us to identify expected enrollment rates, patient drop-out rates, and other threats to the accurate assessment of the course of pain after major joint surgery.
- 2) To estimate the individual variability in pain trajectories over time and to obtain effect size estimates for factors that predict pain trajectory.
- 3) To demonstrate feasibility of providing a pre-surgical teaching intervention in this clinical population.

Methods and Measures

Design

The proposed study is a prospective longitudinal observational study. Patients who are undergoing elective orthopedic surgery: unicompartmental knee replacement, a total knee replacement or total hip replacement will be approached and asked to provide consent to participate in 6 months of observation after their surgery. During this time, participants will not alter their usual treatment in any way (i.e., no treatment algorithms will be altered for this study), but will complete diaries and survey instruments at numerous intervals.

Setting

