The study will be conducted on patients scheduled for major joint orthopedic surgery at Wake Forest University Health Sciences WFUHS. Informed consent and pre-surgical surveys and CBT Intervention will be performed during the preoperative visit in the Joint Replacement Education Conference Room, Preoperative Assessment Clinic or in the Orthopedic Clinic. Perioperative care will be provided at the surgical and post-surgical areas of WFUHS.

Subjects selection criteria

- **Inclusion Criteria**

Adult patients scheduled for elective unicompartmental, total knee replacement, or total hip replacement surgery, will be included. Patients will be American Society of Anesthesiologists physical status 1, 2, or 3.

- **Exclusion Criteria**

We will exclude patients who do not understand English (subjects must be able to read English to answer the questionnaires. The questionnaires are not available in multiple languages), those who are pregnant or within 1 year of childbirth, those with Raynaud's phenomena of the foot, and those with neuropathy of the lower extremities with loss of temperature sensation.

- **Sample Size**

The proposed pilot study aims at identifying effect size estimates and indicators of feasibility. As such, the proposed sample size is not intended to provide definitive estimates of the hypotheses underlying the research. Instead, we propose to enroll N = 75 participants to obtain estimates of drop-out rates (this sample size will allow 95% confidence interval precision of +- 8.2% assuming a 25% drop-out rate) as well as initial estimates of effect sizes for the predictors in the study.

Interventions and Interactions

All patients will complete written informed consent. In addition to review of medical history, indication for major joint surgery and current joint function will be recorded.

The following questionnaires will be completed:

Daily Stress Inventory (DSI, Brantley et al., 1987; 58 items)

Catastrophizing Scale of the Coping Strategies Questionnaire (CATS, 7 items)

McGill Pain Questionnaire-SF (MPQ-SF)

Pre-surgical Intervention:

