After completion of baseline questionnaires (MPQ-SF, DSI, CATS) the Brief CBT Intervention will be viewed by the subject. Upon completion of the presentation, the CATS questionnaire will be administered again. The subject will receive a packet containing "The Power of the Mind," they will be asked to read this information and complete the exercise at the end of the packet. The study staff will call the subject one week after the initial meeting and ask if they have read the packet and will also have the subject to complete the CATS questionnaire again. A postage paid, addressed envelope will be provided for the subject to return the questionnaires to the study team. The questionnaires will be de-identified and only contain subject initials and study identification number.

At Home Diary Assessments

The subject will be given a notebook with paper questionnaires and instructions on how to complete the questionnaires per the schedule below. All participants will complete the assessments in a sequence using one of several methods:

- A. Inpatient evaluation (surgery to discharge): Nursing staff will inquire about the patients pain levels using standard of care methods and assessment tools (e.g., numerical rating scale 0 – 10).
- B. Ecological Momentary assessment (discharge to day 14): The subject will complete the questionnaires in the morning and in the evening.
- C. Once daily (day 15 to day 28): The patient is instructed to complete a diary entry at the end of their day, just prior to going to sleep.
- D. Once weekly (day 29 to day 85): The patient will be called at their home and participate in a brief interview.
- E. Once monthly (day 86 to day 168): The patient will be called at their home and participate in a brief interview once each month.

Each of the assessments will only require about 5 to 10 minutes to complete. At each of the at home assessments the McGill Pain Questionnaire-SF will be administered.

In addition, information from the postoperative care from the orthopedic surgery division will be recorded, including range of joint motion and functional limitations, if any, at the times of routine postoperative clinic visits.

Table 1. A summary of the data collection procedures for the observational study

| Assessment Type | Time (Days) | Questionnaires | Joint Sensory Testing | Thermal Pain Testing | DNIC Protocol | Diary type |

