|-----------------|-------------|----------------|-----------------------|----------------------|---------------|---------------------------------|
| Visit 1 | -14 to 0 | X | X | X | X | NA |
| Post-op | 0 to 3 | | | | | NA |
| Home | 4 to 14 | | | | | Ecological Momentary Assessment |
| Home | 15 to 28 | | | | | Once-daily |
| Home | 29 to 85 | | | | | Weekly |
| Home | 86 to 168 | | | | | Monthly |

Outcome Measure(s)

The primary outcome measure for this study is self-reported pain intensity. To obtain estimates of pain intensity, we will use the McGill Pain Questionnaire - Short Form (MPQ). This instrument has been extensively used to assess pain in a wide variety of settings, and is uniquely suited to our present study in that the items can be completed while in a post-operative setting as well as a daily diary setting.

Analytical Plan

The proposed pilot study aims at identifying effect size estimates and indicators of feasibility. As such, the analytical plan is primarily descriptive in nature. Careful attention will be given to missing data due to any reason, participant withdrawal, and evidence of corrupted or invalid assessments. These threats to data collection will be itemized and descriptive statistics will be used to summarize the rates and expected proportions (with 95% confidence intervals) of measurements that may be lost due to any reason.

To estimate individual variability in the trajectory of pain over time (i.e., healing and diminishing pain reports), and predictors of that trajectory, hierarchical linear modeling (Raudenbush & Bryk, 2002) will be used. The application of HLM in individual change data is well suited for the examination of post surgery pain. Briefly, change trajectories are created for each participant. Because of the nature of the expected change, the trajectories will be modeled using an intercept, slope, and quadratic term. The intercept is coded to represent the baseline level of the pain score (day of surgery). The slope estimates the linear change over time and represents the increase or decrease in the variable. Finally, the quadratic term estimates the acceleration or deceleration over time and reflects changes in the rate of change in pain reporting.

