To assess our specific hypotheses, we will first evaluate the appropriateness of a model that consisted of only intercept (starting value), time, and time-squared as first-level predictors. This first level model describes individual trajectories (change) across time. This model will be evaluated for fit, redundancy, and variability in the parameters and will be reduced to a linear change model if conditions indicate. When a suitable first-level model is developed, and if there is significant variation across participants in either the intercept or change parameters, a second level model will be specified. The second level model will examine the impact of the questionnaires and baseline sensory testing on the trajectories (i.e., linear and quadratic components of the first level model). In all cases, the model coefficients and their standard errors will be of primary interest to inform out later, definitive study.

Risks

Taking part in this research study may involve subject's providing information that they consider confidential or private. Efforts, such as coding research records, keeping research records secure and allowing only authorized people to have access to research records, will be made to keep research related information safe.

Human Subjects Protection

Subject Recruitment Methods

Patients scheduled for unicompartmental knee, total knee replacement, or total hip replacement surgery at WFUHS will be contacted by telephone by our research nurse at least 2 days before surgery. All adult patients scheduled for surgery within the inclusion criteria discussed above will be considered as eligible, regardless of sex, race, or ethnicity. Privacy will be protected by safekeeping and then destruction of surgical posting lists obtained from the Division of Orthopedic Surgery and by the maintenance of all records on password protected computers.

Patient name, age, telephone number, surgical indication, date and procedure scheduled for major joint surgery will be collected to identify and contact potential participants.

This information will be kept on print out in a locked location or on a WFUHS password protected computer. Print out will be shredded and file containing the name will be deleted within 24 hr of declining to participate.

Informed Consent

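### A second joint replacement within the 168 days is neither recorded nor handled, so pain after it is fitted as part of the index recovery

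*Combined protocol and SAP*

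**What the plan says.** **Eligibility.** Under Subjects selection criteria, "Adult patients scheduled for elective unicompartmental, total knee replacement, or total hip replacement surgery, will be included". The exclusions are not understanding English, pregnancy or recent childbirth, and finally "those with Raynaud's phenomena of the foot, and those with neuropathy of the lower extremities with loss of temperature sensation". Subject Recruitment Methods adds that "All adult patients scheduled for surgery within the inclusion criteria discussed above will be considered as eligible". None of this concerns a staged, contralateral or later operation.

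**Follow-up.** Under Design, patients are "asked to provide consent to participate in 6 months of observation after their surgery". The last phase is: "Once monthly (day 86 to day 168): The patient will be called at their home and participate in a brief interview once each month". Routine clinic visits supply range of motion and functional limitations. A further operation is not named as a data item.

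**Outcome and model.** "The primary outcome measure for this study is self-reported pain intensity", measured by the short-form McGill questionnaire (MPQ-SF). The Analytical Plan fits each patient's trajectory with an intercept, a slope and a quadratic, with the intercept set at the day of surgery. The second-level predictors are the questionnaires and baseline sensory testing.

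**Purpose.** Objective 2 is to estimate individual variability in the trajectories and effect sizes for their predictors. The section on the context of the application says the data are to support the power analysis of the later study.

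**The concern.** A patient already booked for the other knee or hip, or who has it replaced during follow-up, stays in the study. That patient then reports pain from a second operation on a clock that started at the first. A single quadratic has no term to absorb a second peak, so the peak bends the fitted curve and enters the between-patient variance of the change terms.

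The planned itemising of missing, withdrawn, corrupted or invalid assessments does not catch this, because a true pain score after another operation is none of those things. The Background treats pain beyond 2 months, and certainly beyond 6, as abnormal. A new peak after about day 60 therefore resembles the phenomenon the programme wants to predict.

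At stake is a main product of the pilot. A slope or quadratic variance that is too high carries into the sizing of the later study. If the dates are not recorded, the affected entries cannot be reliably separated afterwards.

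**Working it through.** **Figures in the plan.** None bears directly on this point: the documents give no second-operation rate, timing or trajectory SD. The one figure attached to the sample size is "this sample size will allow 95% confidence interval precision of +- 8.2% assuming a 25% drop-out rate". With 75 patients the standard error is √(0.25 × 0.75 / 75) = 0.05. The 95% half-width is therefore 1.96 × 0.05 = 9.8 points, and 8.2 is the 90% value (1.645 × 0.05). That is a separate matter and nothing below depends on it.

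**How likely is at least one case?** For an assumed rate r, the expected number is 75r and P(at least one) = 1 − (1 − r)^75.
- r = 1%: 0.75 expected, 53%
- r = 2%: 1.5 expected, 78%
- r = 5%: 3.75 expected, 98%
- r = 10%: 7.5 expected, above 99.9%

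**Schedule.** Taking home entries from day 4, as in Table 1: 22 twice-daily entries (days 4–14), 14 daily (15–28), 9 weekly (29–85) and 3 monthly (placed at days 112, 140 and 168) make 48. In a quadratic fit the 12 entries from day 29 on are a quarter of the data but carry about 62% of the total leverage. The day-168 entry alone has leverage of about 0.70.

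**Why the ratio varies so much.** Suppose a share p of patients has the fitted slope shifted by δ, independently of their true slope. The between-patient variance then rises by p·E[δ²] − p²·(E[δ])². This does not involve the true variance, so the inflation ratio is 1 + (increment / true variance).

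**Simulation (all inputs assumed).** Mean curve 10 + 15·exp(−t/21), intercept SD 5, residual SD 4. A second operation at day s adds 12·exp(−(t − s)/21). Time is in units of 28 days. Each patient gets a quadratic fit, and sampling error is removed from the variance using the known residual SD. There were 8,000 cohorts of 75 per cell. Entries are the mean estimated slope variance, with the ratio to no second operations in brackets.

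| True slope SD / quadratic SD | None | Affected | Days 42–150 | Days 42–90 | Days 84–150 |
|---|---|---|---|---|---|
| 0.6 / 0 | 0.36 | 4 | 0.51 (1.4) | 0.67 (1.9) | 0.37 (1.0) |
| | | 8 | 0.65 (1.8) | 0.94 (2.6) | 0.39 (1.1) |
| 2.0 / 0.3 | 4.00 | 4 | 4.13 (1.03) | 4.31 (1.08) | 4.02 (1.01) |
| | | 8 | 4.28 (1.07) | 4.60 (1.15) | 4.02 (1.01) |

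The increment is nearly the same in both settings. For 8 patients on days 42–150 it is 0.65 − 0.36 = 0.29 and 4.28 − 4.00 = 0.28. Only the denominator changes.

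**A second set of assumptions.** On a 0–10 scale: peak +4 decaying over 28 days, residual SD 1, second-operation rate 10%. With small true SDs (slope 0.4, quadratic 0.05) the variance ratios for slope and quadratic are:
- days 42–168: 1.24 and 1.47
- days 42–90: 1.53 and 1.79
- days 84–168: 1.02 and 1.16

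With larger SDs (0.8, 0.12), the slope ratio lies between 0.99 and 1.11 and the quadratic ratio between 1.05 and 1.15. Intercept variance hardly moves in any scenario (0.98–1.02).

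**Sampling noise.** In the 0.6 / 0 setting, the slope-variance estimate has a cohort-to-cohort SD of about 0.42 with no second operations. The shift is 0.51 − 0.36 = 0.15 for 4 patients on days 42–150, and 0.94 − 0.36 = 0.58 for 8 patients on days 42–90.

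**The case against.** The best defence is that this is a descriptive pilot, which the protocol says is not meant to give definitive estimates. Objective 1 already looks for other threats to assessing the course of pain. The record of orthopedic care is described by examples, so it might include further surgery. The first-level model is checked for fit and for variability. In several scenarios the shift is well below the sampling noise of 75 patients, and monthly calls will often miss a peak that decays within weeks.

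Much of this stands as a limit on size. It does not close the gap. No stated data item captures the date of a second operation, and a fit check on the chosen curve does not say why one patient departs from it. Unlike sampling noise, the shift would not average out with more patients.

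Two stronger readings should be set aside. A reader might infer that the MPQ-SF is not tied to the operated joint. The patient's notebook instructions are not among the documents, so this cannot be judged. A reader might also infer that affected patients would be classed as failed recoveries. The plan has no such class; it models continuous trajectories.

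**Conclusion.** The omission is real, and the direction follows from the model: a second replacement on another joint can inflate the between-patient variance of the slope and quadratic terms, but hardly that of the intercept. With 4 to 8 of 75 patients affected, slope-variance inflation runs from almost nil to a factor of about 2.6. The effect comes mainly from operations at about days 42–90 and nearly disappears for the slope after about day 84. It also becomes small, about 3% to 15% for operations from day 42 on, when true slope variability is large (SD 2.0 per 28 days in the first set of assumptions). Rates, timing, peak and SDs are all assumed.

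A reader might take inflation of half or more as the expected result. That belongs to the small-variability settings and has no support in the documents. Nor would a many-fold rise in quadratic variance mean much where the assumed true value is zero. A reader might also infer biased predictor effects. No calculation here includes a predictor, and a second operation unrelated to the predictors would add noise rather than bias.

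**What to change.** Leave eligibility as it is and make three additions.

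1. **Record.** At the scheduled calls and from the orthopedic records, note the date and joint of any further major joint surgery during the 168 days.
2. **Analyse.** In the hierarchical model, end a patient's trajectory at replacement of a different joint, or add a time-varying term from that date. Choose between these in advance. Keep re-operations on the index joint in the main trajectory and flag them. They may be part of that recovery, and cutting them out could remove poor recoveries informatively.
3. **Report.** Itemise the later entries and the number of patients affected, and give the variance and coefficient estimates with and without those entries. That comparison supplies the size that the documents cannot.

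The cost is one extra question per call, one analysis rule, and a few late observations set aside in the main model.

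### The stated ±8.2% precision for the drop-out rate matches a 90% interval; with 75 patients and 25% drop-out the 95% half-width is ±9.8%

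*Combined protocol and SAP*

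**What the plan says.** Under Subjects selection criteria, the Sample Size item first disclaims inferential aims: "the proposed sample size is not intended to provide definitive estimates of the hypotheses underlying the research". It then gives the reason for the number chosen: "we propose to enroll N = 75 participants to obtain estimates of drop-out rates". In parentheses it adds the precision expected: "this sample size will allow 95% confidence interval precision of +- 8.2% assuming a 25% drop-out rate". The same sentence names a second purpose, first estimates of predictor effect sizes, but attaches no precision to it. No power, significance level, standard deviation or margin appears anywhere in the document.

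The Analytical Plan uses the same confidence level. Lost data are to be summarised as "rates and expected proportions (with 95% confidence intervals) of measurements that may be lost due to any reason". No 90% level, one-sided bound or interval method is mentioned.

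The section on the context of the IRB application says the preliminary data should "allow an accurate power analysis for the size of the proposed study within that grant application". The first objective lists drop-out among the quantities the pilot is meant to establish.

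**The concern.** The sentence contains all its own inputs, so the half-width can be recomputed from it directly, and the result is not the one printed. The stated interval is narrower than 75 patients can deliver at the stated confidence level.

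The precision of the drop-out estimate is the only quantitative support offered for the sample size. A reader judging whether 75 is enough, or a grant reviewer shown the same sentence, would credit the pilot with more information than it will have. When the 95% interval is later computed as the Analytical Plan intends, an observed rate near 25% will give an interval visibly wider than the one promised.

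**Working it through.** **Inputs, all from the Sample Size item**

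- Number enrolled: n = 75, one cohort.
- Drop-out proportion: p = 0.25 ("assuming a 25% drop-out rate").
- Level and form: two-sided 95%, since it is an interval with a ± half-width ("95% confidence interval precision of +- 8.2" percent).

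**Standard error**

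SE = √(p(1 − p)/n) = √(0.25 × 0.75 / 75) = √0.0025 = 0.0500.

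**Reproducing the plan's figure**

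- The quantile implied by the stated half-width is 0.082 / 0.0500 = 1.64, which corresponds to two-sided coverage of 89.9%.
- With the 90% quantile, 1.645 × 0.0500 = 0.0822, or 8.2 points. This reproduces the plan.

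**The figure at the stated level**

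- 1.960 × 0.0500 = 0.0980, or 9.8 points.
- Interval at the planning assumption: 25 ± 9.8 = 15.2% to 34.8%. The plan implies 25 ± 8.2 = 16.8% to 33.2%.
- Ratio of half-widths: 9.8 / 8.2 = 1.20. Difference: 1.6 points.

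**Could another 95% method give 8.2?** An observed rate of exactly 25% would need 18.75 drop-outs, so methods based on counts are evaluated at 18 and 19 of 75. Half-width here means half the interval's total width.

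| Method (95%, two-sided) | Half-width, points |
|---|---|
| Wald, p = 0.25 | 9.8 |
| Wald with t quantile, p = 0.25 | 9.96 |
| Wilson | 9.5 to 9.7 |
| Agresti–Coull | 9.6 to 9.7 |
| Jeffreys | 9.5 to 9.7 |
| Clopper–Pearson (exact) | 10.2 to 10.4 |
| Wald with continuity correction | 10.3 to 10.5 |

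The Wilson interval at 18 of 75 does have a lower arm of 8.2 points (24.0% down to 15.8%), but its upper arm is 10.8, so it cannot be reported as ±8.2.

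**Could a different denominator give 8.2?** Using about 56 completers (75 × 0.75) gives 1.960 × √(0.1875/56) = 11.3 points. Inflating to 75 / 0.75 = 100 gives 1.960 × √(0.1875/100) = 8.5 points. Neither matches.

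**What would make ±8.2 true at 95%?**

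- Sample size: n = 1.960² × 0.1875 / 0.082² = 107.1, so 107 to 108 patients.
- Or, at n = 75, a drop-out rate satisfying p(1 − p) = 75 × (0.082/1.960)² = 0.131, so p ≈ 15.5%.

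**The case against.** The arithmetic is hard to defend; the stronger objection is that it matters little. The study is a descriptive pilot that disclaims definitive estimates. No hypothesis test, stopping rule, feasibility threshold or required precision depends on 8.2, and nowhere does the plan say that ±9.8 would be too wide. The intervals finally reported will be computed from the observed data, so the planning figure cannot bias any result. Drop-out is also only one of two stated reasons for the sample size. The link to the later grant study is an inference: the text speaks of a power analysis without naming drop-out, and effect sizes and between-patient variability are the more direct inputs to it. All of this stands, and it limits the consequence. It does not make the sentence correct.

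Two readings would give 8.2.

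- **One-sided bound.** The quantile 1.645 also belongs to a one-sided 95% bound, but the text says confidence interval and uses ±.
- **Finite-population correction.** With about 250 eligible patients, 9.80 × √(175/249) = 8.2. No such population is stated, and the correction would sit badly with an aim of planning a future study in other patients.

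The plan does not show its calculation, so the 90% explanation is inferred from a match to rounding. The error itself does not depend on that explanation.

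**Conclusion.** The concern holds. With the plan's own inputs, the two-sided 95% half-width is 9.8 percentage points, not 8.2. The claimed precision is overstated by 1.6 points, and the true interval is about 20% wider. This rests on treating the 75 enrolled patients as independent, with all of them in the denominator for drop-out; standard alternatives to the simple formula move the answer only within about 9.5 to 10.5.

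The error should be corrected because it is in the only computed figure supporting the sample size and it flatters the design. The effect on a later study is likely to be small. As an illustration only, assume that study needs 100 completers. Enrolment at the limits of the correct interval would be 100/(1 − 0.152) ≈ 118 to 100/(1 − 0.348) ≈ 153. At the implied limits it would be 100/(1 − 0.168) ≈ 120 to 100/(1 − 0.332) ≈ 150. Nothing here argues against 75 as a pilot size.

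**What to change.** In the Sample Size item, replace 8.2 with 9.8 and leave the sample size, the confidence level and the assumed drop-out rate as they are. It would help to add that the figure is the normal-approximation half-width for a proportion. If the sentence has been copied into the grant application, correct it there too.

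Keeping 8.2 and calling it a 90% interval would be true, but it would put the planning statement at a different level from the 95% intervals in the Analytical Plan, so it is the poorer choice. Raising enrolment to about 108 would deliver 8.2 at 95%, but nothing in the plan shows that this precision is needed.

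The cost is one number in one sentence, with no extra patients, procedures or analyses. The stated precision becomes slightly less favourable.

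### The way the MPQ-SF is given appears to change for every patient at day 29, from self-completed paper to telephone interview, and the planned model would read most of any mode difference as change in pain

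*Combined protocol and SAP*

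**What the plan says.** The section At Home Diary Assessments sets out the home schedule as items A to E. For the paper part: "The subject will be given a notebook with paper questionnaires and instructions on how to complete the questionnaires per the schedule below". Under item B, from discharge to day 14, "The subject will complete the questionnaires in the morning and in the evening". Under item C, days 15 to 28, "The patient is instructed to complete a diary entry at the end of their day, just prior to going to sleep". Item D then reads "Once weekly (day 29 to day 85): The patient will be called at their home and participate in a brief interview", and item E, for days 86 to 168, "The patient will be called at their home and participate in a brief interview once each month".

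The same questionnaire is used throughout the home period: "At each of the at home assessments the McGill Pain Questionnaire-SF will be administered". It is also the instrument for the main endpoint in Outcome Measure(s): "The primary outcome measure for this study is self-reported pain intensity".

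In the Analytical Plan, "the trajectories will be modeled using an intercept, slope, and quadratic term". The slope is interpreted as the rise or fall in pain. The first-level model has only an intercept, time and time-squared, and the second level adds the questionnaires and baseline sensory testing. The first-level model is to be checked for fit, but the only response named is reduction to a linear model. The documents contain no term for mode of administration, no period in which both modes are used, and no statement that the two modes give equivalent scores.

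**The concern.** Every patient appears to move from paper to interview at the same time since surgery, so mode and time are confounded by design. If patients score the MPQ-SF differently when interviewed, the difference shows up as a step at day 29. A smooth curve in time will bend to follow that step.

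This matters because the second objective is to estimate pain trajectories and effect sizes for their predictors, and the Analytical Plan makes the coefficients and standard errors the main input to the later study. The Background treats pain beyond 2 months as abnormal, and all home scores from that period come from the telephone phase.

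**Working it through.** The plan gives no figure on this point, so there is none to reproduce. The check asks how much of a pure mode step the planned time terms would absorb if true pain did not change.

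**Inputs from the documents**
- Paper entries: twice daily on days 4 to 14 (11 × 2 = 22; Table 1 starts the home period at day 4) and once daily on days 15 to 28 (14). Total 36.
- Calls: weekly on days 29, 36, …, 85 (9), then monthly to day 168.

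**Assumptions**
- Three monthly calls, on days 112, 140 and 168. Total calls 9 + 3 = 12; total home assessments 36 + 12 = 48.
- A mode shift of 1 point. All results scale in proportion, so 0.5 point halves them and a negative shift reverses the sign.

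**Projection.** Let m(t) = 0 before day 29 and 1 from day 29. Regress m by least squares on (1, t, t²) and on (1, t) at the 48 times. With complete data, random-coefficient weights give the same coefficients.

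Quadratic fit: m̂(t) = −0.2596 + 0.024445 t − 0.00010416 t².
- Day 4: −0.2596 + 0.0978 − 0.0017 = −0.16
- Day 112: −0.2596 + 2.7378 − 1.3066 = 1.17
- Day 168: −0.2596 + 4.1068 − 2.9399 = 0.91
- False change from day 4 to day 168: 0.91 − (−0.16) = 1.07
- R² = 0.78

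Linear fit: m̂(t) = −0.0431 + 0.009824 t.
- Day 4: −0.0431 + 0.0393 = 0.00
- Day 168: −0.0431 + 1.6505 = 1.61
- False change: 1.61
- R² = 0.63

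The remainder of the step, about a fifth (quadratic) or somewhat over a third (linear), goes to the residual. Starting the home period on day 2 or day 6, or making four monthly calls, keeps R² at 0.78 to 0.80 (quadratic) and 0.62 to 0.65 (linear).

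**Which parameters are affected.** A shift δ shared by all patients adds the same vector, δ × (−0.26, 0.0244, −0.000104), to every patient's coefficients. The mean trajectory moves, but differences between patients do not, so slope variances and predictor coefficients are unchanged. If instead the shift varied by 0.5 point per SD of a predictor, the false predictor effect on slope would be 0.5 × 0.0244 ≈ 0.012 per day. A simulation (75 patients, 300 runs, assumed variances) gave 0.0125, with an SD across runs of 0.0021, so about 6 standard errors.

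**Whether a mode term helps.** The same simulation used a true intercept of 5.00, slope of −0.050 and quadratic of 0.00018, with a mode shift of −1.

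| Model | Intercept | Slope | Quadratic | Mode |
|---|---|---|---|---|
| As planned | 5.27 | −0.075 | 0.00029 | none |
| With mode indicator | 5.01 | −0.050 | 0.00018 | −1.00 |

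The indicator raised the standard error of the mean slope by about 30–40%. Within a participant the rise is about 68%. The recovery holds because the simulated curve really was quadratic.

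**The case against.** Several points on the other side stand.

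- **The mode change is partly inferred.** The notebook is to be used according to a schedule that runs through item E, and Table 1 lists weekly and monthly under diary type. Nothing says whether the patient has the form in hand during a call. The natural reading of items D and E is an oral interview, but the text does not state it, hence the wording that the mode appears to change.
- **The magnitude has no anchor.** The documents give no mode difference and do not say which MPQ-SF score is modelled. Values above 1 point per 1-point shift are overshoot of the fitted curve, and the linear figure applies only if the fit check leads to that reduction.
- **The consequence is limited.** This is a descriptive pilot, the sample size section disclaims definitive estimates, and calls over six months are a sensible retention choice. Scores beyond two months also share one mode, so comparisons between patients in that period are consistent.

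A reader might also infer four stronger things that the documents do not support. First, that the instrument itself changes at day 29: the MPQ-SF is given at every home assessment. Second, that the caller comes from the team that delivered the CBT material and so draws out lower ratings: items D and E name no caller, and nothing indicates a direction. Third, that analysis cannot separate mode from healing: a mode indicator can, if the quadratic shape is right. Fourth, that all predictor effects are biased: this needs a mode effect that varies with the predictor, and no evidence of that is given.

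**Conclusion.** The concern holds in a limited form. As the schedule most naturally reads, mode of administration is confounded with time since surgery, and the model as written would fit most of any mode difference as change in pain. The two false-change figures, 1.1 and 1.6 points per assumed 1-point shift, rest on complete data at the scheduled times. A 0.5-point shift would give about 0.5 and 0.8 points.

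The certain exposure is to the mean trajectory; distortion of slope variances or predictor effects is conditional on an uneven mode effect. This does not invalidate the pilot. It is an avoidable confound in coefficients meant to inform the definitive study, and cheap to reduce beforehand.

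**What to change.** Reword items D and E so that the patient completes an MPQ-SF page from the notebook before each weekly and monthly call. The pages should have the same wording and reference period as the earlier ones; the documents do not state a reference period. The call then prompts completion and records the answers read from the page, and the pages are returned to the study team. This keeps the calls for retention and removes most of the mode difference, though the patient still speaks to a caller.

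Record the mode of every assessment. Report a sensitivity analysis with a first-level mode indicator, stating that it relies on the quadratic shape and widens the standard error of the slope. Because assessment frequency also drops from daily to weekly at day 29, the indicator would pick up both changes together.

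A paired paper-and-telephone assessment at day 28 is unnecessary if one mode is kept, and same-evening recall would pull the paired difference toward zero.

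Cost: about 12 more printed pages per patient (9 weekly + 3 monthly; 13 if there are four monthly calls), slightly more patient burden, and the need to keep the notebook for 6 months.
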